11.3.1 Myelosuppression related events (due to disease or leukemia therapy)

11.3.1.1 febrile or infection episodes not requiring management in the intensive care unit

11.3.1.2 epistaxis or bleeding except for catastrophic CNS or pulmonary hemorrhage

11.3.1.3 anemia, neutropenia, lymphopenia, thrombocytopenia, leukopenia

11.3.2 Disease related events

11.3.2.1 symptoms associated with anemia

11.3.2.1.1 fatigue

11.3.2.1.2 weakness

11.3.2.1.3 shortness of breath

11.3.2.2 electrolyte abnormalities (sodium, potassium, bicarbonate, CO₂, magnesium)

11.3.2.3 chemistry abnormalities (LDH, phosphorus, calcium, BUN, protein, albumin, uric acid, alkaline phosphatase, glucose)

11.3.2.4 coagulation abnormalities

11.3.2.5 disease specific therapy (induction, maintenance, salvage, or stem cell therapy)

11.3.2.6 alopecia

11.3.2.7 bone, joint, or muscle pain

11.3.2.8 liver function test abnormalities associated with infection or disease progression

11.3.2.9 disease progression

11.3.2.10 abnormal hematologic values

11.3.3 General therapy related events

11.3.3.1 catheter related events

11.3.3.2 renal failure related to tumor lysis syndrome or antibiotic/antifungal therapy

11.3.3.3 rash related to antibiotic use

11.3.4 Hospitalization for the management of any of the above expected events

11.4 Abnormal hematologic values will not be recorded on the case report form. For abnormal chemical values, the apogee or nadir (whichever is appropriate) will be reported per course on the case report form.

11.5 Serious Adverse Event Reporting (SAE)

SAE reports should be addressed to DSI Clinical Safety and Pharmacovigilance (CSPV) via email ([contact]) or [contact]). The PI will use Institution's standard forms for reporting SAEs (Serious Adverse Event Reporting (SAVER) form) and pregnancies (Exposure In Utero (EIU) form) in accordance with ICH guidance. DSI's awareness date is the date a SAE is received from the PI. The PI will provide DSI CSPV with final CIOMS report by email ([contact]) or [contact]) in accordance with the following timeframe: (a) Fatal or life-threatening and related SAEs shall be reported within seven (7) calendar days of the date of awareness (b) All other SAEs shall be reported within fifteen (15) calendar days of the date of awareness. SAE submissions to Celgene within 24 hours of becoming aware of the event will be reported by fax to Celgene Drug Safety [contact]). The reporting period ends thirty (30) days after discontinuation of drug, or Completion of subject's participation. In addition, PI must notify Celgene of any SAE that may occur after this time period which the PI believes to be certainly, probably or possibly related to Study Drug. Information not available at the time of the initial report (e.g., an

end date for the adverse event or laboratory values received after the report) must be documented on a follow-up report. A final report to document resolution of the SAE is required.

An adverse event or suspected adverse reaction is considered “serious” if, in the view of either the investigator or the sponsor, it results in any of the following outcomes:

- Death
- A life-threatening adverse drug experience – any adverse experience that places the patient, in the view of the initial reporter, at immediate risk of death from the adverse experience as it occurred. It does not include an adverse experience that, had it occurred in a more severe form, might have caused death.
- Inpatient hospitalization or prolongation of existing hospitalization
- A persistent or significant incapacity or substantial disruption of the ability to conduct normal life functions.
- A congenital anomaly/birth defect.

Important medical events that may not result in death, be life-threatening, or require hospitalization may be considered a serious adverse drug experience when, based upon appropriate medical judgment, they may jeopardize the patient or subject and may require medical or surgical intervention to prevent one of the outcomes listed in this definition. Examples of such medical events include allergic bronchospasm requiring intensive treatment in an emergency room or at home, blood dyscrasias or convulsions that do not result in inpatient hospitalization, or the development of drug dependency or drug abuse (21 CFR 312.32).

- **Important medical events as defined above, may also be considered serious adverse events. Any important medical event can and should be reported as an SAE if deemed appropriate by the Principal Investigator or the INDIND Sponsor, IND Office.**

- All events occurring during the conduct of a protocol and meeting the definition of a SAE must be reported to the IRB in accordance with the timeframes and procedures outlined in “The University of Texas M. D. Anderson Cancer Center Institutional Review Board Policy for Investigators on Reporting Unanticipated Adverse Events for Drugs and Devices”. Unless stated otherwise in the protocol, all SAEs, expected or unexpected, must be reported to the IND Office, regardless of attribution (within 5 working days of knowledge of the event).

- **All life-threatening or fatal events**, that are unexpected, and related to the study drug and those that constitute a clinically important increase in the rate of serious adverse reactions over those listed in the protocol or Investigator Brochure, must have a written report submitted within **24 hours** (next working day) of knowledge of the event to the Safety Project Manager in the IND Office. -

- **Unless otherwise noted, the electronic SAE application (eSAE) will be utilized for safety reporting to the IND Office and MDACC IRB. Serious adverse events will be captured from the time of the first protocol-specific intervention, until 30 days after the last dose of drug, unless the participant withdraws consent. Serious adverse events must be followed until clinical recovery is complete and**

laboratory tests have returned to baseline, progression of the event has stabilized, or there has been acceptable resolution of the event.

- **Additionally, any serious adverse events that occur after the 30 day time period that are related to the study treatment must be reported to the IND Office. This may include the development of a secondary malignancy.**

Reporting to FDA:

- Serious adverse events will be forwarded to FDA by the IND Sponsor (Safety Project Manager IND Office) according to 21 CFR 312.32.

It is the responsibility of the PI and the research team to ensure serious adverse events are reported according to the Code of Federal Regulations, Good Clinical Practices, the protocol guidelines, the sponsor's guidelines, and Institutional Review Board policy.

MDACC Reporting Requirements

All SAEs will be reported to the IRB according to MDACC guidelines. Serious Adverse Events will be submitted electronically via the eSAE system to the IND Office and will be submitted to the FDA by the Safety Coordinator according to 21 CFR 312.32.

Investigator Communication with Supporting Companies:

Any serious suspected unexpected adverse reaction (where SAE is not reported in the Investigator Brochure and is considered to be related to study drug) will be reported to DSI Clinical Safety and Pharmacovigilance (CSPV) via email ([contact]) or [contact]) and by fax to Celgene Drug Safety [contact]) only if related to Vidaza. Information not available at the time of the initial report (e.g., an end date for the adverse event or laboratory values received after the report) must be documented on a follow-up report. A final report to document resolution of the SAE is required.

12.0 STATISTICAL CONSIDERATIONS⁴⁸

12.1 Overview

This is a phase I/II study of two combination therapies in patients with AML or MDS: AC220 + 5-azacytidine, and AC220 + low-dose cytarabine. Patients will be assigned to the two treatments based on physicians' choice. The two treatments will be evaluated separately.

12.2 Phase I

The primary objective of the phase I portion of the study is to determine the MTD of each combination therapy. The dose schedule is listed in table 1 of section 5.2.1. Up to 2 dose levels of AC220 will be tested in each combination with a fixed dose of the other drug. Initially, 6 patients will be treated at dose level1, if ≤ 1 patients experience DLT at dose level1, then 6 subsequent patients will be treated at the next higher dose level, dose level2. If ≤ 1 patients experience DLTs in dose level2, this level will be defined as the MTD and will be used in the phase II portion of the study. If > 1 patients experience DLTs at dose level1, then the 6 subsequent patients will be treated at the next lower dose level, level -1. The MTD is defined as the highest dose at which no more than 1 patient experiences DLTs. For each combination therapy, 12 patients will be evaluated. The total sample size for the phase I portion will be 24.

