- 2.4 Recently, the results of a randomized trial comparing two lower doses of quizartinib were reported. In this trial, patients with relapsed or refractory AML with FLT3 mutation were randomized to receive quizartinib 30 mg or 60 mg orally, daily. A total of 76 patients were enrolled (38 to each arm). The overall composite response rate (CRc, which was the primary endpoint) was identical for the two arms (47%). The overall response rate was slightly higher with 60 mg daily (71%) than with 30 mg daily (61%) because of a higher rate of partial responses in the 60mg arm (24%) compared to the 30 mg arm (13%). QTc prolongation to >500 msec (the dose limit⁹⁸ toxicity for quizartinib) occurred in only 3% with 60 mg and 5% with 30 mg. When comparing these results with a prior study exploring higher doses (90 mg, 135 mg, and 200 mg) it is clear that the rate of CRc is identical at all dose levels with some increase in PR with progressively higher doses. However, QTc prolongation is clearly dose dependent and prolongations >60 msec from baseline occur in 40% or more of the patients treated at doses of 90mg or above, exceeding the threshold of acceptable grade 3 toxicity for the standard definition of MTD. Although these prolongations have been asymptomatic and transient, resolving with lower doses, based on this new data we have decided not to explore a dose level of 90 mg daily and expand 60

mg (i.e., the starting dose level) for the phase 2 portion of the study provided MTD is not exceeded as defined in the protocol section 5.2.5. If MTD is exceeded at this dose level, 30 mg will be explored.

	2689-CL-2004		AC220-002 (Cohort 2)		
	30 mg/day (N = 38)	60 mg/day (N = 38)	90 mg/day (N=57)	135 mg/day (N=67)	200 mg/day (N=12)
Best Response					
CRc Rate	47%	47%	47%	45%	42%
PR Rate	13%	24%	25%	28%	50%
Maximum change in QTcF from baseline (msec)					
≤ 30	50%	44%	9%	9%	0%
> 30 to ≤ 60	47%	36%	46%	51%	8%
> 60	3%	19%	46%	39%	92%

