- 5.2.5** DLT is defined as any clinically significant non-hematologic adverse event or abnormal laboratory value occurring during the first cycle on study unless the event or laboratory value can clearly be determined to be unrelated to AC220 with the following exceptions:
- CTCAE Grade 3 or 4 AST (SGOT) or ALT (SGPT) that resolves to \leq grade 2 in 14 days
 - Grade 3 nausea, vomiting, or diarrhea that can be managed to \leq grade 2 with standard antiemetic or antidiarrheal medications used at prescribed dose within 7 days of onset.
 - Grade 4 vomiting, or diarrhea that can be managed to \leq grade 3 with standard antiemetic or antidiarrheal medications used at prescribed dose within 48 hours of onset.
 - Grade 3 or 4 electrolyte abnormalities will only be considered DLT if possibly related to study drug and not corrected by optimal replacement therapy within 48 hours.
 - Grade 3 biochemical abnormalities of amylase or lipase without evidence of clinical pancreatitis.
 - Grade 3 anorexia or fatigue.
 - Grade 3 or 4 QTc prolongation will constitute DLT as follows: The QTc interval will be calculated by Fridericia's correction factor (QTcF). If the QTc is > 500 msec the EKG must be evaluated within 2 hours in triplicate and if \geq grade 3 QTc prolongation is confirmed this will be considered a DLT.

Hematologic DLT is defined as grade ≥ 3 neutropenia and/or thrombocytopenia with a hypocellular bone marrow lasting for 6 weeks or more after the start of a course in the absence of residual leukemia (i.e., with less than 5% blasts). Anemia will not be considered for the definition of DLT.

- 5.2.5.1** If DLT occurs in $\geq 2/6$ patients, this dose level would exceed the MTD, and an additional 6 patients will be treated at the next lower dose level. The dose level at which 0-1/6 patients experience DLT (but not higher than 60 mg/day) will be used to treat a maximum of 20 patients in each cohort in the phase II portion of the study. If $\geq 2/6$ patients experience DLT at dose level -1 in any arm, dose level -2 may be explored for that arm(s).
- 5.2.5.2** If DLT is observed in 0 or 1/6 in dose level 1, this cohort will be expanded to treat up to 20 patients in the phase II portion of the study. If $\geq 2/6$ patients experience DLT at dose level 1 for any arm of the study, the dose level at which $\leq 1/6$ patients have experienced DLT will be used for the phase II portion of the study for that arm.

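### Section 12.2 escalates to a 90 mg quizartinib cohort after 0-1/6 DLT at 60 mg, whereas Sections 2.4 and 5.2.5 drop that level and take 60 mg into phase II

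*Combined protocol and SAP*

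**What the plan says.** Section 12.2 treats six patients per combination at level 1. With at most one DLT, "then 6 subsequent patients will be treated at the next higher dose level, dose level2"; with at most one DLT at that level, "this level will be defined as the MTD and will be used in the phase II portion of the study". With more than one DLT at level 1, six patients go to level -1. Section 12.2 refers to Table 1 of 5.2.1, where quizartinib is 30 mg at level -1, 60 mg at level 1 and 90 mg at level 2 in both arms. On size it says "For each combination therapy, 12 patients will be evaluated" and "The total sample size for the phase I portion will be 24".

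Section 2.4, citing newly reported dose-comparison data, says "we have decided not to explore a dose level of 90 mg daily". It expands 60 mg for phase II unless the MTD as defined in 5.2.5 is exceeded, and names only a downward step: "If MTD is exceeded at this dose level, 30 mg will be explored". Section 5.2.5.1 says "The dose level at which 0-1/6 patients experience DLT (but not higher than 60 mg/day) will be used" for phase II. Section 5.2.5.2 says "If DLT is observed in 0 or 1/6 in dose level 1, this cohort will be expanded to treat up to 20 patients".

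Section 5.1 describes a third scheme: a target of dose level 0 and a first group of six at level -1. No table contains a level 0, and 5.2.1.1, 5.2.3, 5.2.7 and 12.2 all start at level 1 (60 mg).

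**The concern.** The MTD of each combination is the phase I primary objective. For one observable result, 0-1/6 DLT at 60 mg, the protocol prescribes two incompatible actions, and no section says which governs. The conflict falls on the branch that is followed when the starting dose is tolerated.

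The level at issue is the one the sponsor dropped for safety. The table in Section 2.4 shows QTcF increases above 60 msec in 19% of patients at 60 mg and 46% at 90 mg, with a composite response rate of 47% at both (the two doses come from different studies). Someone working from the statistical section alone would open a cohort that Section 2.4 rejects, and could carry into phase II a dose that 5.2.5.1 prohibits. The stated phase I size has the same origin, since it assumes that every arm enrols a second cohort.

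**Working it through.** **Step 1: the two rules side by side (each arm, six patients per level).**

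| Result | Section 12.2 | Sections 2.4 and 5.2.5 |
|---|---|---|
| 0-1/6 DLT at level 1 (60 mg) | six patients at level 2 (90 mg) | 60 mg goes to phase II |
| 0-1/6 DLT at level 2 | 90 mg is MTD and phase II dose | no such cohort; phase II capped at 60 mg/day |
| ≥2/6 DLT at level 1 | six patients at level -1 (30 mg) | 30 mg |
| ≥2/6 DLT at level -1 | not stated | level -2 may be explored |

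The first two rows conflict. Section 2.4 gives a reason based on new data and refers to 5.2.5 for the MTD, so 12.2 is the outlier.

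**Step 2: the stated size.** 6 patients × 2 levels = 12 per combination; 12 × 2 combinations = 24. This reproduces 12.2, which therefore always counts a second cohort per arm, at 90 mg or 30 mg.

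**Step 3: the size under 5.2.5.1-5.2.5.2.** An arm uses 6 patients after 0-1/6 DLT at level 1 and 12 after ≥2/6. Over two arms the total is 12, 18 or 24. This excludes replacements under 5.2.5.4 and any level -2 cohort, and counts a six-patient level -1 cohort as phase I.

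**Step 4: illustration.** The documents give no DLT rates for these combinations, so p is assumed and taken as equal in the two arms. P(0-1/6) = (1-p)^6 + 6p(1-p)^5.

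| Assumed p at 60 mg | P(0-1/6), per arm | Expected patients in 90 mg cohorts under 12.2 = 12 × P(0-1/6) | Expected phase I total under 5.2.5 = 12 + 12 × P(≥2/6) | P(total = 24) = P(≥2/6)² |
|---|---|---|---|---|
| 0.10 | 0.886 | 10.6 | 13.4 | 0.01 |
| 0.20 | 0.655 | 7.9 | 16.1 | 0.12 |
| 0.30 | 0.420 | 5.0 | 19.0 | 0.34 |

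If 12.2 were followed literally, the chance per arm that 90 mg becomes the phase II dose is the product of P(0-1/6) at the two levels. For assumed rates at (60 mg, 90 mg):
- (0.10, 0.20): 0.580
- (0.10, 0.30): 0.372
- (0.20, 0.30): 0.275
- (0.20, 0.40): 0.153

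**Step 5: sensitivity to 5.2.5.3.** After 2/6 DLT at level 1, that section treats 26 additional patients at 30 mg in phase II. If this means no separate phase I cohort at level -1 when exactly 2/6 have DLT, only ≥3/6 adds six patients. P(≥3/6) is 0.016, 0.099 and 0.256 at p = 0.10, 0.20 and 0.30, and the expected totals become 12 + 12 × P(≥3/6) = 12.2, 13.2 and 15.1.

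**The case against.** The strongest reply is that the operational text is already protective. Section 5.2.5.1 carries an explicit cap, 2.4 explains it, and 5.2.4 requires a cohort summary to go to the Medical Monitor before any change of cohort. This stands to the extent that a 90 mg cohort is avoidable, and the probabilities above are not forecasts of harm. It does not remove the conflict: 5.2.4 requires a summary but does not say which rule applies, and the statistical section still states the wrong one.

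Two stronger readings are tempting. A reader might infer that 2.4 also rules out raising an individual patient to 90 mg, so that 6.5.5 should be capped at 60 mg. The documents do not support this. Section 2.4 concerns the level to explore and expand for phase II and does not mention individual escalation. Section 6.5.5 sets its ceiling at 90 mg/day, 9.2.5.1 schedules EKGs for patients raised to 90 mg, and the titles of Tables 1 and 2 cover escalation as well as reduction. Removing that option would be a clinical decision, not a consistency correction.

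A reader might also infer that without a level 2 cohort individual escalation to 90 mg becomes impossible, because 6.5.4 requires at least three patients followed for 28 days without DLT at the next higher level. That is one reading only. Section 6.5 is headed for patients at level -1 or lower, for whom the next level from -1 is 60 mg. Only items 6.5.1 to 6.5.3 end in a conjunction, so 6.5.5 may be a separate provision with its own QTc and response conditions.

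**Conclusion.** Section 12.2 is wrong as written and needs correction, because it states a dose-decision rule for the phase I primary objective that contradicts 2.4, 5.2.5.1 and 5.2.5.2. The conclusion comes from comparing the texts and does not depend on any assumed DLT rate. Its size is up to 12 patients in 90 mg cohorts under 12.2 against none under 2.4 and 5.2.5. The fixed total of 24 is a ceiling for two levels per arm, on the counting conditions in step 3. Section 5.1 is out of line with every other statement of the starting level. Whether 6.5.4 governs the step from 60 to 90 mg is unclear; if it does, the condition could not be met once the level 2 cohort is gone.

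**What to change.** **Section 12.2, dose rule.** Delete the level 2 step and state:
- six patients at level 1 (60 mg);
- 0-1/6 DLT makes 60 mg the phase II dose;
- ≥2/6 sends six patients to level -1 (30 mg);
- 0-1/6 there makes 30 mg the phase II dose;
- ≥2/6 there means level -2 may be explored.

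**Section 12.2, size.** Replace 12 per combination and 24 overall with 6 or 12 per combination and 12 to 24 in total. Say that this excludes replacements under 5.2.5.4 and any level -2 cohort, and counts a six-patient level -1 cohort as phase I.

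**Section 5.1.** Change the start from level -1 to level 1 and remove level 0.

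**Individual escalation.** Sections 6.5.5 and 9.2.5.1 can stay. Mark level 2 in Tables 1 and 2 as individual escalation only, and state whether 6.5.4 applies to the step from 60 to 90 mg. If it is meant to apply, its condition needs rewording.

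**Cost.** A wording amendment with no added patients. On the counting conditions above, phase I stays at 24 or shrinks. Phase II sizes, priors and stopping boundaries in 12.3 are unchanged.

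### After 0-1 DLTs in 6 patients at 60 mg, section 12.2 escalates to 90 mg and can make it the phase II dose, while 2.4 and 5.2.5 expand at 60 mg and cap phase II there

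*Combined protocol and SAP*

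**What the plan says.** Section 12.2 (Phase I) starts 6 patients per combination at dose level 1. With at most 1 DLT, "then 6 subsequent patients will be treated at the next higher dose level, dose level2". With at most 1 DLT there, "this level will be defined as the MTD and will be used in the phase II portion of the study". With more than 1 DLT at level 1, the next 6 go to level -1. It evaluates 12 patients per combination and concludes: "The total sample size for the phase I portion will be 24". Tables 1(a) and 1(b) set quizartinib at 30 mg for level -1, 60 mg for level 1 and 90 mg for level 2.

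Section 2.4, which follows the cytarabine background, reviews dose-ranging data and states "we have decided not to explore a dose level of 90 mg daily". It expands 60 mg instead, "provided MTD is not exceeded as defined in the protocol section 5.2.5", with 30 mg as the fallback.

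Section 5.2.5.1 limits the dose carried into phase II: "but not higher than 60 mg/day". Section 5.2.5.2 reads: "If DLT is observed in 0 or 1/6 in dose level 1, this cohort will be expanded to treat up to 20 patients". Section 5.2.5.3 covers exactly 2/6 DLTs at level 1 and sends a further 26 patients to level -1 in phase II.

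Section 5.1 differs again. It treats the first 6 patients at level -1 and refers to a level 0 that Table 1 does not contain. Sections 5.2.1.1, 5.2.3 and 5.2.7 all start at level 1 or 60 mg.

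**The concern.** One result, 0-1 DLTs in 6 patients at 60 mg, leads to two incompatible next steps. The statistical section opens a 90 mg cohort; the treatment plan goes straight to phase II at 60 mg. No reading satisfies both, and nothing says which section governs.

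At stake is the phase II dose of a QT-prolonging drug. Section 2.4 gives its reason for dropping 90 mg: QTcF rose by more than 60 msec in 46% of patients at 90 mg against 19% at 60 mg, while the composite response rate was 47% at both (single agent, compared across studies). The DLT definition in 5.2.5 does not name that change. Its QTc criterion is different: "If the QTc is > 500 msec the EKG must be evaluated within 2 hours in triplicate", and it counts only if grade 3 or worse is confirmed. A 90 mg cohort could therefore pass 12.2 while showing the effect for which 2.4 rejected the dose.

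**Working it through.** **1. The two paths side by side (each combination separately)**

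| Result at 60 mg | 12.2 | 2.4 and 5.2.5 |
|---|---|---|
| 0-1/6 DLTs | 6 more at 90 mg; 90 mg is the phase II dose if 0-1/6 | expand 60 mg; phase II cap 60 mg/day |
| 2 or more of 6 | 6 more at level -1 (30 mg) | 6 more at level -1 (30 mg) under 5.2.5.1 |

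The paths differ only in the first row, where 60 mg is tolerated.

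**2. The plan's own figure**

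Under 12.2 each combination uses two levels of 6 patients, whether it moves up or down: 2 × 6 = 12. Two combinations give 2 × 12 = 24, so the stated total reproduces.

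**3. How likely 12.2 is to adopt 90 mg**

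Let X be the number of DLTs among 6 patients, binomial with rate p. Then P(X ≤ 1) = (1−p)^6 + 6p(1−p)^5.

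- p = 0.10: 0.5314 + 0.3543 = 0.886
- p = 0.20: 0.2621 + 0.3932 = 0.655
- p = 0.30: 0.1176 + 0.3025 = 0.420
- p = 0.40: 0.0467 + 0.1866 = 0.233

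The two sections diverge with probability 0.886, 0.655 or 0.420 at an assumed 60 mg DLT rate of 10%, 20% or 30%.

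P(90 mg adopted under 12.2) = P(X ≤ 1 at the 60 mg rate) × P(X ≤ 1 at the 90 mg rate):

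| Assumed DLT rate at 60 mg | Assumed DLT rate at 90 mg | P(90 mg is the phase II dose), 12.2 | Same, 2.4 and 5.2.5 |
|---|---|---|---|
| 10% | 20% | 0.886 × 0.655 = 0.58 | 0 |
| 10% | 30% | 0.886 × 0.420 = 0.37 | 0 |
| 20% | 30% | 0.655 × 0.420 = 0.28 | 0 |
| 20% | 40% | 0.655 × 0.233 = 0.15 | 0 |

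The rates are assumptions; the documents report none for either combination. They rise with dose because the concern with 90 mg is dose-related toxicity.

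**4. Phase I size under 5.2.5**

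An arm that passes at 60 mg needs 6 patients; one that steps down once needs 12. With level -2 not opened, two arms need 12 to 24. Expected size per arm = 6 + 6 × (1 − P(X ≤ 1)):

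- 10%: 6 + 6 × 0.114 = 6.7
- 20%: 6 + 6 × 0.345 = 8.1
- 30%: 6 + 6 × 0.580 = 9.5

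The stated 24 is thus a ceiling on this path, not a fixed size.

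**The case against.** The strongest reply is that the intention is clear. Section 2.4 is a reasoned decision based on newer data and names 5.2.5 as the MTD rule. Table 1 labels level 1 as both starting and target dose, 5.2.5.1 has an explicit cap, and 5.1 is one stray paragraph that errs towards a lower dose. Section 12.2 looks like text that was not updated. That is a fair inference, and staff would probably follow 5.2.5. It lowers the practical risk, but 12.2 still sets the dose rule and phase I size in the statistical section.

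Safeguards also apply at any dose. Section 5.2.4 sends a cohort summary to the Medical Monitor before cohorts change, 6.3 reduces quizartinib above 480 msec and interrupts it above 500 msec, 9.2.5 requires triplicate ECGs in the first three cycles, and 12.3 monitors DLTs in phase II. These limit harm to a patient but do not decide which dose phase II should use.

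A reader might infer that the DLT rule would fail to stop 90 mg, or might treat the 46% as a DLT rate. The documents support neither. They give no rate of QTc above 500 msec at 90 mg, and the table in 2.4 reports maximum change with no stated time limit, whereas DLTs count only in the first cycle. An investigator could also judge a rise of more than 60 msec clinically significant under the general DLT wording. What stands is that this change is not a named DLT.

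A reader might also take level 2 in the tables, or the 90 mg provisions in 6.5.5 and 9.2.5.1, as part of the contradiction. They concern individual patients, and 2.4 can be read as a decision about cohorts only. They authorise neither a 90 mg cohort nor a 90 mg phase II dose, and whether individual 90 mg dosing is kept is a separate clarification.

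**Conclusion.** The contradiction is real and should be corrected. On the result that allows 60 mg to go forward, 12.2 can select a phase II dose that 2.4 rejects and 5.2.5.1 forbids. For the assumed pairs of DLT rates shown, the probability that 12.2 ends at 90 mg is 0.15 to 0.58, against 0 under 2.4 and 5.2.5. These figures assume that 12.2 is followed as written and that patients' DLTs are independent with a common rate at each level.

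The sample-size consequence is smaller: 24 remains a valid maximum if level -2 is not opened, but it should not be stated as fixed. The error in 5.1 is clear from the sections it contradicts.

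A reader might go further and recompute total enrolment for the whole trial. The documents do not settle that. Phase I enrols regardless of FLT3 status, and 12.3 counts phase I patients treated at the same dose towards the Cohort 2A azacitidine groups but has no such clause for Cohort 2B.

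**What to change.** Rewrite 12.2 to follow 2.4 and 5.2.5, for each arm:

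- Treat 6 patients at level 1 (60 mg).
- If 0-1/6 have a DLT, expand level 1 into phase II.
- If 2 or more of 6 have a DLT, treat 6 at level -1 (30 mg) before expanding there. Word the 26 further patients in 5.2.5.3 as these 6 plus 20, so that it agrees with 5.2.5.1.
- Keep the phase II dose at or below 60 mg/day.
- State phase I as 6 to 12 evaluable patients per arm, 12 to 24 in total, with more only if level -2 is opened.

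In 5.1, replace both the reference to level 0 and the start at level -1 with level 1.

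Leave individual escalation to 90 mg (6.5.5, 9.2.5.1 and level 2 in the tables) outside this change and clarify it separately.

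The cost is amendment wording. Phase II sizes and stopping boundaries stay as they are. The one loss is that neither combination will have 90 mg cohort data, which 2.4 already accepts.
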